6.5. Patient Compliance

Patient compliance will be tracked through the seizure and medication diary. Parent/caregiver are to record daily seizure frequency and type in addition to study medication and non-study AED administration. Compliance with IP treatment will be assessed by inspecting the seizure and medication diary entries and returned supplies with queries as necessary. Parent/caregiver will be re-educated on the importance of adhering to daily seizure, IP and non-study AED recording as needed. Patients that fall below 80% compliance at 2 consecutive visits during the maintenance period will not be in the Per-Protocol (PP) population.

7. STUDY PROCEDURES

7.1. Study Assessments

See Schedule of Assessments (Table 1 and Table 2) for details regarding scheduled assessments and procedures in this study.

Study Assessments can be conducted at the institution of the site Investigator or remotely at the patient's home. All assessments can be conducted remotely with the use of telemedicine video tools used by the site staff; and providing traveling nurses to take vital signs, draw blood samples, and collect specimens. [REDACTED] and ECGs can be completed by a mobile vendor that is contracted to perform these tasks.

7.2. Study Procedures (Part A: Treatment Period)

7.2.1. Screening Period

7.2.1.1. Screening (Visit 1, Week -4)

Additional procedures/assessments to be completed during the screening period may include the following:

- Informed consent from parent/LAR (or patient assent)
- Demographics and medical history
- Review of inclusion/exclusion criteria
- Review previous genetic testing results to evaluate pathogenic or likely pathogenic *TSC1* or *TSC2* variant. If genetic testing has not previously been performed, then a biological sample will be obtained to complete genetic testing at the sponsor's designated lab.
Note: Tuberous Sclerosis Complex diagnosis does not require pathogenic *TSC1* or *TSC2* mutations if the clinical criteria are met.
- Seizure Identification and Diagnostic Review Form (SIF/DRF) (Epilepsy Study Consortium)

- Vital signs (to include blood pressure [BP], heart rate [HR], respiratory rate [RR], and body temperature).
- Height and weight. Length will be measured if height cannot be obtained.
- Physical, neurological, and developmental examination (developmental examination is limited to pediatric patients 2 to 17 years of age, inclusive)
- Clinical laboratory tests (chemistry and hematology)
- Urinalysis (an attempt should be made to collect a urine sample at this screening visit. Otherwise, the urine sample can be collected at baseline.)
- Drug screen (plasma) for THC and CBD. If the screening drug test is positive, the patient can be retested after two weeks.
- Serum pregnancy test for all girls/women of childbearing potential
- Tanner staging
- Concomitant AED review and levels if per standard of care
- [REDACTED]
- AEs
- Seizure and medication diary set up and review. Caregiver given seizure diary and instructions for use.

A screen failure is a patient for whom informed consent/assent has been obtained and has failed to meet the inclusion criteria and/or met at least one of the exclusion criteria and has not been administered the IP.

Patient rescreening is allowed as agreed by the sponsor and the investigator unless there is a general concern for patient safety or an inability for the patient to become eligible (e.g., GNX allergy, sensitivity or exposure, non-TSC and/or other ineligible epilepsy, chronic prohibited medical condition or treatment). Subsequent screening should take place at least 30 days from the patient's last visit.

7.2.2. Baseline (Visit 2, Week 0 + 4 days)

The 4 weeks between the Screening Visit and the Baseline Visit can be no less than 28 days and no more than 32 days. The following study procedures/assessments are to be completed prior to IP administration:

- Review of inclusion/exclusion criteria
- Medical history review
- Review genetic testing results for patients that were screened without previous genetic testing results and had a genetic test performed at the sponsor's designated lab
- SIF/DRF (Epilepsy Study Consortium) approval
- Vital signs (to include BP, HR, RR, and body temperature)

- Weight
- Physical, neurological, and developmental examination (developmental examination is limited to pediatric patients 2 to 17 years of age, inclusive)
- ECG
- Clinical laboratory tests (chemistry and hematology)
- Urinalysis (If the urine sample was not collected at screening, it must be collected at baseline)
- Drug screen (plasma) for THC and CBD
- Serum pregnancy test for all girls/women of childbearing potential
- Concomitant AED review and levels if per standard of care
- AEs
- Seizure and medication diary review
- [REDACTED]
- CGI-C (parent/caregiver/LAR identified behavioral target). During the baseline visit, the investigator and parent/caregiver/LAR will decide on a domain and identify the specific behavior that the patient exhibits that denotes the domain. This behavior will be used at subsequent visits to assess change after the initiation of IP.
- CGI-I (parent/caregiver/LAR and clinician)
- Columbia-Suicide Severity Rating Scale (C-SSRS) (baseline form) for patients \geq 7 years old if appropriate. Otherwise clinical judgment will be used.
- Dispense IP

7.2.3. Telephone Follow-up (Day 1, 2 and 3 + 1 days)

A telephone follow-up visit will be conducted each of the 3 (\pm 1) days after the Week 0 Baseline Visit to assess the following:

- AEs
- Seizure and medication diary review

7.2.4. Titration Period (Visit 3, Week 1 \pm 3 days)

The following study procedures/assessments will be completed at Week 1 (\pm 3 days):

- Vital signs (to include BP, HR, RR, and body temperature)
- Weight
- Physical, neurological, and developmental examination (developmental examination is limited to pediatric patients 2 to 17 years of age, inclusive)
- ECG

- Clinical laboratory tests (chemistry and hematology)
- Urinalysis
- Concomitant AED review and levels if per standard of care
- AEs
- Seizure and medication diary review

7.2.5. Titration Period (Phone Follow-ups, Weeks 2, 3, and 4 ± 3 days)

A telephone follow-up visit will be conducted at Weeks 2, 3, and 4 (\pm 3 days) to assess the following:

- AEs
- Seizure and medication diary review

7.2.6. Maintenance Period (Visits 4 and 5, Weeks 5 and 12 ± 3 days)

The following study procedures/assessments will be completed at Weeks 5 and 12 (\pm 3 days):

- Vital signs (to include BP, HR, RR, and body temperature)
- Weight
- Physical, neurological, and developmental examination (developmental examination is limited to pediatric patients 2 to 17 years of age, inclusive)
- ECG
- Clinical laboratory tests (chemistry and hematology)
- Urinalysis
- Drug screen (plasma) for THC and CBD (Visit 5 [Week 12])
- Serum pregnancy test for all girls/women of childbearing potential
- IP PK sample (Visit 4 [Week 5], between 1-5 hours after last IP dose and Visit 5 [Week 12], between 4-8 hours after last IP dose)
- Concomitant AED review and levels if per standard of care
- [REDACTED]
- AEs
- Seizure and medication diary review
- [REDACTED]
- CGI-C (parent/caregiver/LAR identified behavioral target)
- CGI-I (parent/caregiver/LAR and clinician)
- C-SSRS (since previous visit). Only for patients \geq 7 years old if appropriate, otherwise clinical judgement will be used.

- Dispense IP

7.2.7. Maintenance Period (Phone Follow-up, Week 9 ± 3 days)

A telephone follow-up visit will be conducted at Week 9 (\pm 3 days) to assess the following:

- AEs
- Seizure and medication diary review

7.2.8. Taper and Safety Visits (Visit 5a, Week 16 ± 3 days)

For patients who do not continue into study Part B, the following assessments will be completed after 2 weeks of taper and 2 weeks after completion of treatment (\pm 3 days):

- Vital signs (to include BP, HR, RR, and body temperature)
- Tanner staging
- AEs
- Seizure and medication diary review
- C-SSRS (since previous visit). Only for patients \geq 7 years old if appropriate, otherwise clinical judgement will be used.

7.3. Study Procedures (Part B: OLE Period)

7.3.1. First OLE Visit (Visit 5, Week 12)

Patients who complete Part A with a seizure reduction of \geq 35% compared to the 4-week baseline period and who do not have any other contraindications for continued treatment will continue to be treated with GNX in the OLE period (Part B) of the study. Ganaxolone patients will continue GNX treatment at the dose that they were on at the completion of Part A. The following study procedures/assessments will be completed during the final maintenance period visit in Part A (Visit 5, Week 12):

- Confirm patient OLE eligibility (\geq 35% reduction in seizure frequency)
- Vital signs (to include BP, HR, RR, and body temperature).
- Height and weight. Length will be measured if height cannot be obtained.
- Physical, neurological, and developmental examination (developmental examination is limited to pediatric patients 2 to 17 years of age, inclusive)
- ECG
- Clinical laboratory tests (chemistry and hematology)
- Urinalysis
- Drug screen (plasma) for THC and CBD
- Serum pregnancy test for all girls/women of childbearing potential
- IP Population PK sample (drawn when convenient during the visits)

- Concomitant AED review and levels if per standard of care
- [REDACTED]
- AEs
- Seizure and medication diary review
- [REDACTED]
- CGI-C (parent/caregiver/LAR identified behavioral target)
- CGI-I (parent/caregiver/LAR and clinician)
- C-SSRS (since previous visit). Only for patients \geq 7 years old if appropriate, otherwise clinical judgement will be used.
- Dispense IP

7.3.2. OLE Period and Final OLE Visit or Taper Visit (Visits 6, 7, and 8 [or Early Discontinuation], Weeks 20, 28, and 36 [or Early Discontinuation] \pm 7 days)

The following study procedures/assessments will be completed during the OLE period of the study at Visits 6, 7, and 8 (\pm 7 days):

- Vital signs (to include BP, HR, RR, and body temperature)
- Weight
- Physical, neurological, and developmental examination (developmental examination is limited to pediatric patients 2 to 17 years of age, inclusive)
- ECG (Visit 7, Week 28 and Visit 8, Week 36)
- Clinical laboratory tests (chemistry and hematology)
- Urinalysis (Visit 7, Week 28 and Visit 8, Week 36)
- Drug screen (plasma) for THC and CBD (Visit 7, Week 28)
- Serum pregnancy test for all girls/women of childbearing potential
- Tanner staging (Visit 8, Week 36)
- IP PK sample (drawn when convenient during the visits)
- Concomitant AED review and levels if per standard of care
- [REDACTED]
- AEs
- Seizure and medication diary review
- [REDACTED]
- CGI-C (Visit 8, Week 36, parent/caregiver/LAR identified behavioral target)
- CGI-I (Visit 8, Week 36, parent/caregiver/LAR and clinician)

- C-SSRS (since previous visit). Only for patients \geq 7 years old, otherwise clinical judgement will be used.
- Dispense IP

7.3.3. Telephone Follow-up (Weeks 16, 24 and 32 \pm 7 days)

A telephone follow-up visit will be conducted at Weeks 16, 24, and 32 (\pm 7 days) of the OLE period to assess the following:

- AEs
- Seizure and medication diary review

7.3.4. Safety Follow-up Post Taper (Visit X, 2 Weeks Post Last Dose \pm 3 days)

The following study procedures/assessments to be completed during the Safety Follow-up Post Taper Visit (\pm 3 days):

- Vital signs (to include BP, HR, RR, and body temperature)
- Physical, neurological, and developmental examination (developmental examination is limited to pediatric patients 2 to 17 years of age, inclusive)
- Clinical laboratory tests (chemistry and hematology)
- Urinalysis
- Serum pregnancy test for all girls/women of childbearing potential
- IP PK sample (drawn when convenient during the visits)
- Concomitant AED review and levels if standard of care
- AEs
- Seizure and medication diary review

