**Pharmacokinetic Assessments:**

The pharmacokinetic (PK) population will include all patients who have received at least 1 dose of GNX and who have had at least 1 sample collected and a valid bioanalytical result obtained. The samples will be drawn between 1 and 5 hours or between 4 and 8 hours after the last dose during Part A and Part B. Pharmacokinetic analyses will be limited to listing of concentrations because sufficient concentration-time data will not be available for noncompartmental analyses such as maximum plasma concentration (C_{max}), area under the concentration versus time curve (AUC), or time of maximum concentration (t_{max}). Pharmacokinetic data from this study may be used for a Population PK analyses to be conducted separately from this study and reported separately. Further details will be provided in the Statistical Analysis Plan.

Safety and Tolerability Assessments:

Safety and tolerability will be assessed by monitoring vital signs (blood pressure [BP], heart rate [HR], respiratory rate [RR], body temperature, electrocardiograms (ECGs), clinical laboratory tests (hematology, chemistry and urinalysis), physical, neurological, and developmental examinations, Columbia-Suicide Severity Rating Scale (C-SSRS) if appropriate and frequency, type, and severity of adverse events (AEs) during Part A and Part B. Height and weight will also be measured.

Statistical Methods:

The intent-to-treat (ITT) population comprises all patients who received at least one dose of IP. The ITT population will be the primary population for efficacy analyses. The Per-Protocol (PP) population includes all ITT patients without major protocol violations (defined prior to database lock). Safety will be reported in all patients.

Since this is an OL proof of concept study, no inferential statistical testing will be conducted, and all efficacy outcomes will be descriptive.

Primary Endpoint: Definition and Analysis:

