-4 (Screening Visit – Start of Baseline)	0 (Baseline Treatment Visit)	Day 1	Day 2	Day 3	1	2, 3, 4	5	9	12	16 Taper/Safety Visits ^p	
Visit Windows	+ 4 days		± 1 day		± 3 days	± 3 days	± 3 days	± 3 days	± 3 days	± 3 days	
VISIT	Visit 1 ^a	Visit 2 ^o	Phone Follow-up	Phone Follow-up	Phone Follow-up	Visit 3	Phone Follow-up	Visit 4	Phone Follow-up	Visit 5	Visit 5a
Informed Consent ^b	X										
Demographics & Medical History	X	X ^s									
Inclusion/Exclusion Criteria	X	X									
Genetic testing	X ^c	X ^r									
Seizure Identification and Diagnostic Review Form (Epilepsy Study Consortium)	X	X									
Vital Signs (BP, HR, RR, and body temperature)	X	X			X		X		X		X
Height / weight	X ^d	X ^e			X ^e		X ^e		X ^e		
Physical/Neurological/Developmental Exam ^t	X	X			X		X		X		
ECG		X			X		X		X		
Clinical Laboratory Tests ^f	X	X			X		X		X		
Urinalysis	X ^g	X ^g			X		X		X		
Drug Screen ^h	X	X							X		
Pregnancy Test (WCBP) ⁱ	X	X					X		X		

Table 1: Schedule of Assessments - Part A

WEEK	Part A										
	Screen/Baseline		Titration and Maintenance								
-4 (Screening Visit – Start of Baseline)	0 (Baseline Treatment Visit)	Day 1	Day 2	Day 3	1	2, 3, 4	5	9	12	16 Taper/Safety Visits ^p	
Visit Windows	+ 4 days		± 1 day		± 3 days	± 3 days	± 3 days	± 3 days	± 3 days	± 3 days	
VISIT	Visit 1 ^a	Visit 2 ^o	Phone Follow-up	Phone Follow-up	Phone Follow-up	Visit 3	Phone Follow-up	Visit 4	Phone Follow-up	Visit 5	Visit 5a
Tanner Staging	X										X
IP PK							X ^j		X ^j		
Concomitant AED Review and Levels if Per Standard of Care ^k	X	X			X		X		X		
Adverse Event	X	X	X	X	X	X	X	X	X		X
Seizure and Medication Diary Review ^l	X ^l	X	X	X	X	X	X	X	X		X
CGI-C - Target Behavior		X ^m					X		X		
CGI-I (caregiver)		X					X		X		
CGI-I (clinician)		X					X		X		
C-SSRS (baseline form) ^q		X									
C-SSRS (since previous visit) ^q							X		X		X
Dispense GNX ⁿ		X					X		X		

AED = antiepileptic drug, BP = blood pressure, CBD = cannabidiol, CGI-C = Caregiver Global Impression of Change, CGI-I = Clinical Global Impression – Improvement, C-SSRS = Columbia-Suicide Severity Rating Scale, D/C = discontinuation, ECG = electrocardiogram, [REDACTED], GNX = ganaxolone, HR = heart rate, IP = investigational product, LAR = legally authorized representative, PK = pharmacokinetic, RR = respiratory rate, THC = tetrahydrocannabinol, WCBP = women of childbearing potential.

Table 1: Schedule of Assessments - Part A

WEEK	Part A										
	Screen/Baseline		Titration and Maintenance								

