Weight ^a	X		X		X		X	
Physical/Neurological/Developmental Exam	X		X		X		X	X
ECG	X				X		X ^d	
Clinical Laboratory Tests ^b	X		X		X		X	X
Urinalysis	X				X		X	X
Drug Screen	X				X			
Pregnancy Test (WCBP) ^c	X		X		X		X	X
Tanner Staging							X ^d	
IP PK ^e	X		X		X		X	X
Concomitant AED Review and levels if per standard of care	X		X		X		X	X

Table 2: Schedule of Assessments - Part B

		Part B							
		Final Part A Visit/ First Part B Visit	Open-Label Extension (Visits will be every 8 weeks with a telephone follow-up in-between)					Final OLE Visit or Taper Visit	Safety Follow-up Post-taper
WEEK		12	16	20	24	28	32	36 or early D/C	2 weeks post last dose
Visit Windows			± 7 days	± 7 days	± 7 days	± 7 days	± 7 days	± 7 days	± 3 days
VISIT		Visit 5	Phone follow-up	Visit 6	Phone follow-up	Visit 7	Phone follow-up	Visit 8 (Week 36) ^g or Visit X (early D/C)	Visit X
[REDACTED]		[REDACTED]						[REDACTED]	
Adverse Event		X	X	X	X	X	X	X	X
Seizure and Medication Diary Review		X	X	X	X	X	X	X	X
[REDACTED]		[REDACTED]						[REDACTED]	
CGI-C - Target Behavior		X						X	
CGI-I (caregiver)		X						X	
CGI-I (clinician)		X						X	
C-SSRS (since last visit form) ^f		X		X		X		X	
Dispense GNX		X		X		X		X	

AED = antiepileptic drug, BP = blood pressure, CGI-C = Caregiver Global Impression of Change, CGI-I = Clinical Global Impression – Improvement, C-SSRS = Columbia-Suicide Severity Rating Scale, D/C = discontinuation, ECG = electrocardiogram, [REDACTED], GNX = ganaxolone, HR = heart rate, IP = investigational product, OLE = open-label extension, PK = pharmacokinetic, RR = respiratory rate, WCBP = women of childbearing potential.

- Weight will be measured at every visit, except the safety follow-up visit.
- Chemistry and Hematology.
- Serum pregnancy test is required for all girls/women of childbearing potential.
- Conduct at Week 36/Visit 8 or the last open-label extension visit if prior to Week 36/Visit 8.
- PK samples can be drawn when convenient during the study visits.

Table 2: Schedule of Assessments - Part B

Part B									
	Final Part A Visit/ First Part B Visit	Open-Label Extension (Visits will be every 8 weeks with a telephone follow-up in-between)						Final OLE Visit or Taper Visit	Safety Follow-up Post-taper
WEEK	12	16	20	24	28	32	36 or early D/C	2 weeks post last dose	
Visit Windows		± 7 days	± 7 days	± 7 days	± 7 days	± 7 days	± 7 days	± 3 days	

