4.5. Discontinuation of Patients

A patient may withdraw - or their parent/LAR may withdraw the patient - from the study at any time for any reason without prejudice to their future medical care by the physician or at the hospital. The investigator or sponsor may withdraw the patient at any time (e.g., in the interest of patient safety). The investigator is encouraged to discuss withdrawal of a patient from IP with the medical monitor when possible.

If the IP is discontinued at any time, patients should follow the 2-week taper schedule unless otherwise medically indicated such as drug-induced rash. If the patient discontinues during the maintenance period of Part A, evaluations listed for Taper and Safety Visit (Section 7.2.8) are to be performed as completely as possible. If the patient discontinues during the OLE period (Part B), evaluations listed for the Taper Visit (Section 7.3.2) and Safety Follow-up Post Taper

Visit (Section 7.3.4) are to be performed as completely as possible. Comments (spontaneous or elicited) or complaints made by the patient must be recorded in the source documents. The reason for termination, date of stopping IP, and total amount of IP taken must be recorded in the electronic case report form (eCRF) and source documents. Discontinuation of IP due to AEs must also be reflected on the AE eCRF page.

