6.2.2.1. De-escalation Period

Any patient who discontinues IP treatment should undergo a 2-week drug de-escalation (taper) period, unless otherwise medically indicated such as drug-induced rash. The schedule will be dependent on the maintenance dose. Typically, doses will be reduced by 15 mg/kg/day or 450

mg/day every 3 days until the patient is completely off IP. Patients should then return for a post-taper safety follow-up visit.

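### No C-SSRS is scheduled at the Part B post-taper visit, although the corresponding Part A visit has one and no reason is given

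*Protocol*

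**What the plan says.** **Part A.** Protocol 7.2.8 covers patients who do not continue into Part B and times Visit 5a (Week 16) as follows: "the following assessments will be completed after 2 weeks of taper and 2 weeks after completion of treatment". Its five items include "C-SSRS (since previous visit). Only for patients" aged 7 or over if appropriate, with clinical judgement otherwise. Table 1 and SAP Appendix A mark this form at Weeks 5, 12 and 16.

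**Part B.** Protocol 7.3.4 describes the visit 2 weeks after the last dose. After "The following study procedures/assessments to be completed during the Safety Follow-up Post Taper Visit" it lists vital signs, examinations, laboratory tests, urinalysis, pregnancy test, a PK sample, AED review, adverse events and diary review. In Table 2 the row beginning "C-SSRS (since last visit form" is marked at Visits 5, 6, 7 and 8 (or early discontinuation) and is blank in the post-taper column. SAP Appendix B is the same.

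**Leaving Part B.** Protocol 4.5 calls for two sets of evaluations: "If the patient discontinues during the OLE period (Part B), evaluations listed for the Taper Visit (Section 7.3.2) and Safety Follow-up Post Taper". Section 6.2.2.1 sets the taper: "Any patient who discontinues IP treatment should undergo a 2-week drug de-escalation (taper) period", unless medically indicated otherwise.

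**Status of the scale.** The Synopsis includes among the safety measures "Columbia-Suicide Severity Rating Scale (C-SSRS) if appropriate and frequency, type, and severity of adverse events (AEs) during Part A and Part B". SAP 1.2.4 lists the C-SSRS as a safety endpoint for both parts, and SAP 4.3.6.1 summarises it by visit. Neither document explains the different treatment of the two post-taper visits.

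**The concern.** The two visits do the same job: each is the safety check after the drug has been tapered and stopped. One carries a form that looks back over the withdrawal window and the other does not. Long-term safety in Part B is a secondary objective (Protocol 2.2.2), and the C-SSRS is one of the measures named to serve it. As scheduled, the Part A by-visit C-SSRS summary can contain a post-withdrawal assessment, while the Part B summary can contain none unless a site adds one. A reader of the report would have no sign that an absence of Part B findings stops at, or shortly before, the end of dosing.

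**Working it through.** The check needs no statistical calculation. It sets the schedules side by side and counts weeks.

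**Step 1: where the C-SSRS is scheduled around withdrawal.**

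| | Stops after Part A | Stops in Part B |
|---|---|---|
| Last visit with C-SSRS before the post-taper visit | Visit 5, Week 12 (7.2.6, Table 1) | Visit 8, Week 36, or early discontinuation (7.3.2, Table 2) |
| Post-taper visit | Visit 5a, Week 16 (7.2.8) | Visit X, 2 weeks after last dose (7.3.4) |
| C-SSRS at post-taper visit | Yes (7.2.8, Table 1, SAP Appendix A) | No (7.3.4, Table 2, SAP Appendix B) |

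The Part B omission appears in three places that agree, and the list in 7.3.4 contains no redacted item. It is not an artefact of the PDF.

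**Step 2: length of the window.** Inputs are a taper of 2 weeks (6.2.2.1) and a post-taper visit 2 weeks after the last dose (7.2.8, 7.3.4).

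- Part A leaver: C-SSRS at Week 12; taper ends at about 12 + 2 = Week 14; C-SSRS again at 14 + 2 = Week 16. The 4 weeks are covered by the second form.
- Part B leaver at Week 36, Taper Visit before the taper: C-SSRS at Week 36; taper ends at about 36 + 2 = Week 38; Visit X at about 38 + 2 = Week 40, with no C-SSRS. Uncovered: 40 − 36 = about 4 weeks.
- Part B leaver, Taper Visit at the end of the taper: only the off-drug interval is uncovered, about 2 weeks.
- Part B leaver stopping without a taper for medical reasons: if the early-discontinuation visit falls at the stop, again about 2 weeks.

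**Step 3: which timing is likelier.** The protocol does not place the Taper Visit relative to the taper. Two features suggest that it comes first: drug is still dispensed there (7.3.2, Table 2), and 4.5 pairs it with a separate post-taper visit. Dispensing is not conclusive, because patients may stay in the extension beyond Visit 8. The 4-week figure is therefore the likelier reading, and 2 weeks is the lower one.

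**Step 4: who is affected.** Part B patients who stop and to whom the scale applies. The documents give no count. Enrolment is about 30 (Protocol 9.4), which is a ceiling: not all enter Part B, entry age starts at 2, and the form is tied to age 7 or over and to appropriateness.

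**The case against.** The strongest reply is that Part B is internally consistent (7.3.4, Table 2 and SAP Appendix B agree) and that the two post-taper visits differ in other ways. Visit 5a has no laboratory tests, urinalysis, pregnancy test, PK sample or physical examination, and the Part B visit has them all, so the visits may not have been meant to match. That is fair, and it is why an explicit justification would also settle the point. It does not supply a reason, though. The Part B visit is the fuller of the two, so burden does not explain leaving out a questionnaire. Another item in the same column is also unreconciled: Protocol 7.7.3 includes weight at the post-taper visit, while Table 2 footnote a excludes it.

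A reader might infer several stronger things that the documents do not support:

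- **That suicidality goes unassessed during Part B withdrawal.** Visit X collects adverse events and includes physical and neurological examination, and AE and SAE collection runs through follow-up (8.1, 8.2.4). Ideation or behaviour could be reported that way. Only the scheduled structured scale is missing.
- **That every Part B patient who stops is affected.** The age and appropriateness limits rule this out.
- **That Part A leavers are fully covered.** They have one retrospective form under the same limits, and 4.5 assigns the Visit 5a evaluations only to discontinuation in the maintenance period.
- **That a comparison of Part A and Part B leavers is spoiled.** None is planned. The SAP summarises the parts descriptively and separately, with an overall summary.
- **That longer exposure makes withdrawal riskier.** The safety background in Protocol 1.2 reports no suicidality or withdrawal signal, and early Part B leavers have well under 36 weeks of exposure.

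**Conclusion.** The point holds as an unexplained asymmetry in the schedule of a named safety endpoint. For Part B leavers to whom the C-SSRS applies, about 4 weeks of taper and off-drug time have no scheduled structured suicidality assessment, or about 2 weeks if the Taper Visit falls at the end of the taper or no taper is given. In that window suicidality would be captured only through AE reporting or at a site's discretion. The 4-week figure assumes the nominal 2-week taper and a Taper Visit held before it. The omission itself rests on no assumption. The primary efficacy analysis and the AE tables are not affected. The change is worth making because the gap lies in a stated safety measure, following the plan as written would leave it open, and it is cheap to close.

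**What to change.** Reconcile Protocol 7.3.4, Table 2 and SAP Appendix B with Protocol 7.2.8 and Table 1, so that the existing since-previous-visit form covers the post-taper window in both parts for the same patients. In the same edit, state whether the Taper Visit falls at the start or the end of the taper, so that the period each form covers is clear.

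If the difference is intended, give the reason in the protocol and add a sentence to SAP 4.3.6.1 saying that Part B C-SSRS summaries exclude the withdrawal period.

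The first route costs one short questionnaire at a visit that already takes place, plus an amendment line in each document. The by-visit summary in SAP 4.3.6.1 would simply gain a row. The second route costs two sentences.
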